#### chosen sets within cohorts.

The attraction of the above method is that it gives quantitative results with implications for whether subsequent examinations are needed and if so, at what intervals, without making parametric assumptions about the distribution of progression rates or explicitly estimating test sensitivity. However, it is worthwhile to carry out some parametric multistate modelling, partly for internal consistency checking and partly for further interpretation. For example, for those for whom there is evidence of an increasing chance of polyps according time to subsequent examination, an estimate of the test sensitivity would indicate what proportion of these might be detected and treated by improved performance of the baseline examination, and what proportion occur de novo and therefore need repeat examinations to detect them.

#### c. Formal multistate models

We propose exponential distributions for incidence and progression of adenomas. This means that at a subsequent examination t years after the baseline, the proportion observed with at least one polyp would be

where  $\lambda_1$  and  $\lambda_2$  are the rates of incidence of new intermediate risk adenomas and of progression of these to CRC respectively. P is the proportion of polyps newly observed at subsequent examination which were not there at baseline. It is estimable by its relationship to the observed proportion P0 of negative results at baseline and the test sensitivity S:

Thus for a cohort of intermediate-risk adenomas at baseline examination we also need to know the numbers with negative results at baseline in order to estimate the relevant parameters. The variation in practice in terms of t, the time between examinations, gives the necessary degrees of freedom to estimate all three parameters S,  $\lambda_1$  and  $\lambda_2$ .

The estimates of P,  $\lambda_1$ ,  $\lambda_2$  and S can then be made from the observed data, and subsequently used to estimate the proportions picked up at examination before progression to malignancy. It will give a third and most formal criterion for choosing suitable intervals between examinations. The analysis will be augmented with further analyses as follows

- 1 Covariate adjustment for age, sex and where available family history
- 2 Subgroup analysis, such as by sex and polyp class
- 3 More detailed models, such as the five state: no disease- small polyp- large polypspreclinical cancer- clinical cancer
- 4 Sensitivity analyses for a range of plausible underlying incidence rates

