#### 2.8 Sample size

For simplicity, we base our sample size requirements on the comparison of the rates of detection at first follow-up at two different intervals, using the heterogeneity in practice with respect to follow-up intervals. A reasonable possibility might be 5% of subjects with an intermediate or high risk lesion at first follow-up at 4-6 years and 3% at 2-4years . For 90% power to detect this at 5% significance level in a two-sided test, we would need a total of 4,400 subjects with at least one follow-up examination. For second or subsequent follow-up, we might stipulate the more relaxed criterion of wishing to estimate the detection rate within 1% in either direction. If we anticipate 3% of subjects to have intermediate or high-risk lesions at second or subsequent follow-up, this would require 1,200 subjects with at least two follow-up up endoscopies.

We might also stipulate a sample size to give relatively low coefficients of variation of S, the test sensitivity, and  $\lambda_2$ , the rate of progression to clinical CRC, in order to compare different intervals between follow-up with respect to rates of cancers that would accrue. In order to use these with confidence to predict effects of different follow-up policies, we require a high degree of precision in estimation of S and  $\lambda_2$ . We therefore stipulate that both have coefficients of variation of no more than 30% (i.e. the standard error of each estimate has magnitude no larger than 30% of the value of the estimate).

Closed form estimation is not possible for these quantities and it is difficult to predict the variability of our estimates. Work by Chen et al  and Wong et al  suggest that with around 30 events, CV's of 30% or less can be achieved if the rate of progression is small (0.2 per annum or less). However, we would be likely to wish to stratify or at least introduce covariates, which would reduce the precision. We therefore aim to recruit cohorts with a total of 60 CRCs.

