Stryker et al  found rates of progression in untreated adenomas suggestive of a  $\lambda_2$  of around 0.01 for progression to CRC. Atkin et al  studied a wide case mix of treated polyps at entry (corresponding to the situation in this project), and suggests a rate of around 2 per thousand per year after colonoscopy overall and around 4.5 per thousand per year for the high-risk subgroup. Thus, in the literature, the rate ranges from 2 to 10 per thousand per year.

If we assume that the underlying risk of CRC in our cohorts is considerably higher than the population risk, but that the relative risk might be brought down by the protection of endoscopic examination to between one and two times the population risk in males aged 50 or over, we would have a figure of between 2.5 and 5 endpoints per thousand per year. In total, therefore, we would require between 12,000 and 24,000 person-years of follow-up after endoscopy episodes. Assuming an average of four years observation, this would require recruiting cohorts to a total of 6,000 subjects. We propose as a failsafe strategy to recruit 10,000.

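### Section 2.9.1c relies on variation in examination interval to estimate progression to CRC, but polyp findings carry too little information on it; CRC outcomes need to be in the same likelihood

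*Combined protocol and SAP*

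**What the plan says.** Section 2.9.1c assumes exponential times to a new adenoma (rate λ1) and from adenoma to CRC (rate λ2). The modelled follow-up quantity is given by "the proportion observed with at least one polyp would be" followed by an equation that is missing from the available text. For the baseline examination, "we also need to know the numbers with negative results at baseline" so that S and P (which separates new from missed lesions) can be related. The section then states that the differing intervals t between examinations, as they arise in practice, supply what is needed: this variation "gives the necessary degrees of freedom to estimate all three parameters", namely S, λ1 and λ2. It describes no CRC outcome for this model. Section 2.9.2 carries the same modelling to later examinations.

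Section 2.8 sets the precision wanted for S and λ2: a CV of at most 30%, meaning that "the standard error of each estimate has magnitude no larger than 30% of the value of the estimate". It supports this by event counts, saying that "with around 30 events, CV's of 30% or less can be achieved if the rate of progression is small (0.2 per annum or less", and aims for 60 CRCs. For the size of λ2 it concludes that "the rate ranges from 2 to 10 per thousand per year".

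Section 2.9.3 describes clinical CRCs after examination as a complement to the other analyses, where available, and takes them in steps up to formal multistate models.

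**The concern.** Section 2.8 obtains the precision of λ2 from CRC events, whereas section 2.9.1c credits it to the spread of examination times. Enough distinct values of t gives enough equations, but that is not the same as enough information. λ2 affects polyp prevalence only by removing lesions that have already become CRC, and at the stated rates few have done so by the next examination.

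An analyst who codes 2.9.1c as written would leave out the data on which section 2.8 bases its target. The section calls its result the third and most formal criterion for choosing intervals, and λ2 determines how many cancers each interval is predicted to allow. Section 2.3.3 also takes the jointly estimated transition rates and test characteristics into the intermediate-risk economic model.

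**Working it through.** **1. The plan's own sizing for λ2 (section 2.8).** Person-years = CRCs / rate: 60/0.005 = 12,000 and 60/0.0025 = 24,000. At four years each, 24,000/4 = 6,000 subjects. These match the plan. With events counted directly, CV ≈ 1/√events: 1/√30 = 18.3% and 1/√60 = 12.9%. The 30% target is therefore reasonable if λ2 is estimated from CRCs and the person-time at risk with an adenoma is known.

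**2. How much λ2 moves polyp prevalence.** The fraction of lesions leaving the adenoma state in 5 years is at most 1 − exp(−5λ2), which is 1.0% at λ2 = 0.002 and 4.9% at 0.010.

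Because the equation is missing, I assumed the model that the text describes:

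π(t) = S{P·λ1/(λ1 − λ2)·[exp(−λ2t) − exp(−λ1t)] + (1 − P)·exp(−λ2t)}

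Here q is the true lesion-free proportion at baseline, P0 = q + (1 − q)(1 − S), and P = q/P0.

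With S = 0.8, λ1 = 0.012 and P0 = 0.97, detection is about 3.4% at 3 years and 5.2% at 5 years, close to the 3% and 5% in section 2.8. Raising λ2 from 0 to 0.010 lowers 5-year detection by 0.15 percentage points; raising it to 0.0045 lowers it by 0.07. The standard error of a 5% rate in 2,200 subjects (half of the 4,400 in section 2.8) is √(0.05 × 0.95/2,200) = 0.46 points. In all 7,046 patients with a follow-up colonoscopy (Appendix 1.0) it is √(0.05 × 0.95/7,046) = 0.26 points.

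**3. CV of λ2 from expected Fisher information.** Polyp findings are binomial and intervals are evenly spread. From the documents: λ2 = 0.002 to 0.010 and n = 4,400 or 7,046. Assumed: S 0.8 to 0.9, λ1 0.012 or 0.03, P0 0.60 or 0.97. A second set takes S about 0.85 and 5-year detection from 5% to 49%.

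| Data and setting | CV of λ2 |
|---|---|
| Polyp findings, all three free, n = 7,046, intervals 1-10 years | 460% to 6,200% |
| Same, intervals 2-6 years | 2,100% to 29,000% |
| Same, n = 4,400, both interval ranges | 580% to 37,000% |
| All three free, n = 7,046, 5-year detection 5% to 49% | 114% to 28,000% |
| S and λ1 treated as known, n = 4,400 or 7,046 | 44% to 1,440% |
| S and λ1 known, higher detection, λ2 = 0.010 | 25% to 60% |
| Joint likelihood with CRC outcomes added | 9% to 88%, often under 30% |

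The upper ends shift somewhat with the exact spacing of intervals. With all three parameters free, no setting came near 30%. The lowest, 114%, needs λ2 = 0.010, intervals over 1-10 years and detection near 49%.

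**The case against.** The strongest reply is that the plan as a whole does use CRCs. Section 2.8 aims for 60, its update reports about 120, 170 and 50 by risk group (340 in all), section 2.9.3 takes clinical CRCs to multistate models, section 2.3.3 refers to long-term follow-up data, and 2.9.1c lists a five-state extension with preclinical and clinical cancer. This stands to the extent that the data exist and the plan intends to use them. It does not repair 2.9.1c. Section 2.9.3 is complementary and conditional on availability, writes no likelihood shared with S and λ1, and is not referred to in 2.9.1c.

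Other points also stand. The section uses the baseline-negative proportion and does not say that variation in t is sufficient alone. In the assumed model the information matrix is not singular, so the remark about degrees of freedom is not algebraically false. The equation and several inputs are reconstructed. If the modelled finding is any adenoma (the background cites 30% to 50% recurrence) and S and λ1 were known, the CV could reach 25% at λ2 = 0.010, but the plan estimates all three. The low value 0.002 comes from CRC incidence after polyp removal rather than lesion progression, although the plan pools the two; at 0.010 the CV still exceeds 100%.

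The stakes are limited too. Section 2.9.1 presents multistate modelling partly as a consistency check, questions 6 to 8 rest on Cox models and CRC incidence, and the intermediate-risk economic analysis has been reported. The additional economic analysis does not cite section 2.9 for its inputs.

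**Conclusion.** The point holds for sections 2.9.1c and 2.9.2. With S, λ1 and λ2 all free, polyp findings give a CV of λ2 above 100% in every setting tried, and usually many hundreds to thousands of per cent, against a target of 30%. The exact figures depend on a reconstructed equation and on assumed S, λ1, P0 and intervals; the failure to reach 30% does not, across the ranges tried.

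A reader might infer that λ2 is unidentifiable, or that the study cannot estimate it at all. The documents support neither. The parameters are formally identifiable in the assumed model, and 60 CRCs would meet the target under the simple calculation above. Nor does the point undermine the sample size or the Cox analyses. The defect is that the model in 2.9.1c is not joined to the CRC data from which section 2.8 obtains its precision. Because section 2.9 remains the analysis plan for the All Adenomas study (Appendix 1.0), it is worth correcting.

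**What to change.** In 2.9.1c and 2.9.2, replace the statement about variation in t with one joint likelihood for S, λ1 and λ2. Its contributions per patient should be:

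- no lesion found at examination;
- adenoma found at examination;
- CRC found at examination;
- clinical CRC, at its diagnosis date;
- for patients with no follow-up examination, CRC follow-up time, censored if no CRC occurs. In the intermediate-risk cohort this is 11,944 − 7,046 = 4,898 patients, who would otherwise contribute nothing.

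Cross-refer to sections 2.8 and 2.9.3, so that the source of precision for λ2 is the same throughout. Report the CV of λ2 actually achieved, overall and in any stratum used to choose intervals, because the 30% target may still be missed where CRCs are few (the joint calculation ranged up to 88%).

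The cost is SAP wording and additional likelihood coding. No new data are needed: Appendix 1.0 lists cancer incidence and registration data as part of the study database.

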#### 2.9.2 Second and subsequent follow-up

Analysis of findings at second and subsequent follow-up will closely parallel those of first follow-up with the slight complication of the need to consider their joint association with both baseline and first follow-up results. As for part (a) of the analytic strategy, simple analysis of rates of polyps by time since last examination, the major difference will be stratification by the two previous examinations.

For part (b), the logistic regression, the endpoint (y-) variable will be the finding at second or subsequent follow-up and the x-variables studied will be firstly as before the time since last examination and baseline. Then we will augment the model with findings at first follow-up examination to see if these significantly improve prediction of findings at second and subsequent follow-up. The logistic regression model would now be

where  $x_1$  represents time since last examination,  $x_2$  size of polyp at last examination,  $x_3$  multiplicity of polyps at last examination,  $x_4$  presence of polyps at first follow-up examination etc.

The formal multistate modelling in (c) will be carried out to model sensitivity, incidence and

progression after the first follow-up. The results will give a further indication of the desirability or otherwise of subsequent follow-up beyond the first one and of changing the frequency of examination after the first follow-up.

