# 2.9 Statistical analysis

#### 2.9.1. Baseline and first follow-up screen analyses

a. Simple analysis of rates of events since last examination

In the first instance we will use simple descriptive statistics to summarise findings at first follow-up colonoscopy in relation to time since baseline examination, and consider the detection rates of advanced adenomas at subsequent examination stratified by findings at baseline examination, interval since baseline examination, age and sex. There is particular a priori interest in comparing intervals of less than 4 years (i.e. roughly 3 years) with intervals of 4-6 years (roughly 5 years). The stratification by baseline findings is particularly important, as there is likely to be heterogeneity, which in turn should inform policy.

We will be dealing with the detection of adenomas in the large bowel at first follow-up examination. These will be relatively common premalignant conditions (in a population all of whom have already had at least one such lesion). Practice in terms of interval to follow-up examination is not standard, and we will use this variability in practice to deduce the relative effects of different policies. If there are larger prevalences observed with longer intervals, this would suggest a suitable interval at which a sufficiently large harvest of polyps will result to render the practice effective and economical. On the other hand, a constant detection rate with time since last examination might lead us to suspect that de novo lesions were relatively rare and the constant harvest is of lesions missed at the baseline examination.

The above approach is attractive because of its simple, empirical nature. We would, however, wish to quantify our qualitative conclusions, and to extrapolate to intervals other than those for which we have data, for example to almost immediately after baseline examination, in relation to the issue of missed lesions. For this, more formal statistical analyses would be necessary.

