# b. Logistic regression to relate findings at first follow-up with findings at baseline and to the interval between the two

The goal here is to formally estimate the combined effects of findings at baseline and time since baseline on the findings at subsequent examination. In the first instance we shall consider the findings at subsequent endoscopic examination by time since previous examination and the size, multiplicity, grade and sub site of polyps found at baseline examination. To study different outcomes at subsequent examination, we shall fit a number of logistic regressions with different outcomes, including:

- 1 Any adenoma
- 2 Multiple adenomas
- 3 Single advanced adenoma
- 4 Multiple and advanced adenoma

The logistic regressions will be of the form

where  $x_1$  represents time since last examination,  $x_2$  size of polyp at last examination,  $x_3$  multiplicity of polyps at last examination, and so on. Host factors such as age, gender and any personal or family history data available can also be built into these analyses. The results of these can be used to determine subgroups which, for example, have very low rates of polyps at subsequent examination and may not need further surveillance beyond the baseline, and to determine optimal interval times for those who do need further surveillance.

In addition, we shall estimate any modifiers of the effect of time since last examination. For example, there may be a subgroup with  $\beta_1$  close to zero, despite a non-negligible harvest of polyps at subsequent examination. This would suggest that the polyps were present but missed at the baseline examination, and may point to a group that only needs a single subsequent examination. This can be verified by using data on those subjects with more than one repeat examination. In addition, all analyses with implications for policy beyond the baseline examination will be subject to cross-validation across cohorts and between randomly

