### 2.9.3 Analysis of colorectal cancer occurrence after endoscopic examination

The analyses above will be complemented by analyses of subsequent clinical CRCs in the follow-up period where available. Such events are rare and estimates will therefore be imprecise, but the analysis will add some value to the exercise, by enabling us to assess the trade-off between harvest of polyps at subsequent examination and expected number of cancers occurring before the subsequent examination. Again the analysis will proceed in steps of increasing complexity, beginning with simple description of rates of cancers by time since and findings at last examination, through regression modelling to formal multistate models.

We will assess the absolute risk of CRC using Kaplan-Meier curves and will compare the incidence of CRC to that expected in the general population, both in the absence and in the presence of surveillance. We will use Cox proportional hazards models to assess the effect of surveillance on the risk of CRC, with the number of follow-up visits included as a time-varying covariate.

The models will also be used to assess the relationship between patient, polyp and procedural characteristics at baseline and CRC risk. We will use univariable models to estimate unadjusted hazard ratios and will use multivariable models to estimate the effect of surveillance adjusted for patient, polyp and procedural characteristics and to identify independent predictors of future CRC risk. The risk factors identified in the multivariable models will then be used to aid in the creation of distinct subgroups. These subgroups will then be scrutinised to determine whether in any subgroup the CRC risk after baseline is low enough relative to the general population to not warrant surveillance. Conversely, in subgroups that do appear to benefit from surveillance, the results will be examined to see whether the risk of CRC becomes low enough after a certain number of exams in order for surveillance to safely cease.

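### Interval effects come from unrandomised hospital practice, but the analysis text names neither hospital nor a clustered variance, and only the Cox models name procedural covariates, so interval estimates risk confounding and understated standard errors

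*Combined protocol and SAP*

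**What the plan says.** Section 2.9.1(a) notes that follow-up intervals are not standardised and continues: "we will use this variability in practice to deduce the relative effects of different policies". Appendix 1.0, clarification (a), makes the hospital dataset the All Adenomas study database. Section 2.8.1 plans on 20 hospitals.

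The covariates named differ by model:

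- **Logistic models, 2.9.1(b):** time since examination and "the size, multiplicity, grade and sub site of polyps found at baseline examination". The text adds "Host factors such as age, gender and any personal or family history data available can also be built into these analyses". The list of terms is left open.
- **Multistate models, 2.9.1(c):** "Covariate adjustment for age, sex and where available family history".
- **Logistic models, 2.9.2:** the same kind of terms plus first follow-up findings; "the endpoint (y-) variable will be the finding at second or subsequent follow-up".
- **Cox models for colorectal cancer (CRC), 2.9.3:** "multivariable models to estimate the effect of surveillance adjusted for patient, polyp and procedural characteristics".
- **High-risk group, end of 2.9.3:** one-year against longer first intervals, compared on CRC incidence in crude groups, with no adjustment stated.

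Of a subgroup with an interval coefficient near zero but a worthwhile yield, 2.9.1(b) says: "This would suggest that the polyps were present but missed at the baseline examination". It adds that such a group may need only one further examination.

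**The concern.** When practice variation is the exposure, whatever drives practice can confound it. Hospitals may differ in miss rates, in reporting and in recall policy, so hospital can influence both the interval and the yield. Baseline examination quality can do the same for individual patients: a poor examination may lead to an early repeat that finds a lot, which raises the yield at short intervals and flattens the slope. The plan would then attach a specific meaning to that flat slope. The multistate models are exposed too, because 2.9.1(c) relies on variation in the time between examinations to identify test sensitivity and the incidence and progression rates.

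Patients from one hospital also share its yield level. If intervals cluster by hospital as well, a standard error computed as if patients were independent is too small, and subgroups look better separated than they are. These analyses feed question 8 (appropriate intervals) and the choice of groups who might have less surveillance.

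**Working it through.** **1. The plan's own sizes (section 2.8).**

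- Later follow-up, 3% estimated to within 1 point: n = 2² × 0.03 / 0.01² = 1,200. This matches the plan (multiplier 2, Poisson variance).
- First follow-up, 5% against 3%, 90% power, two-sided 5%: per arm (1.960 + 1.282)² × (0.05 + 0.03) / 0.02² = 10.507 × 0.08 / 0.0004 = 2,101.5. With d = 0.02, the continuity correction n/4 × (1 + √(1 + 4/(n·d)))² gives 2,200.3, rounded up to 2,201 per arm or 4,402 in total, against the stated 4,400. The usual pooled formula gives 4,032.

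Both figures treat subjects as independent, with no allowance for hospital.

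**2. Hospital clustering of the interval effect.** Appendix 1.0 reports 7,046 intermediate-risk patients with at least one follow-up. With 20 hospitals, m = 7,046 / 20 = 352.3. The design effect is DE = 1 + (m − 1) × ICC(yield) × ICC(interval), where ICC(interval) is the share of interval variation lying between hospitals. Coverage of a nominal 95% interval is 2Φ(1.96/√DE) − 1. The documents give no ICCs; those below are assumptions. Power is for 5% against 3% with 7,046 patients split equally.

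| ICC(yield) | ICC(interval) | DE | true SE / naive SE | coverage | power |
|---|---|---|---|---|---|
| – | – | 1.00 | 1.00 | 95% | 99% |
| 0.01 | 0.05 | 1.18 | 1.08 | 93% | 98% |
| 0.01 | 0.10 | 1.35 | 1.16 | 91% | 96% |
| 0.01 | 0.20 | 1.70 | 1.30 | 87% | 91% |
| 0.02 | 0.20 | 2.4 | 1.55 | 79% | 79% |

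For scale, at a mean yield of 4%, ICC ≈ 0.04 × 0.96 × SD², where SD is the between-hospital standard deviation on the log-odds scale. ICCs of 0.01 and 0.02 correspond to SDs of about 0.51 and 0.72, which is substantial variation. SDs of 0.2 and 0.4 correspond to ICCs of about 0.0015 and 0.006, where the effect on standard errors is smaller.

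**3. Hospital confounding of the interval effect.** Simulation with 20 hospitals, hospital SD 0.2 to 0.4, ICC(interval) 0.1 to 0.3, and correlation +0.5 or −0.5 between a hospital's yield level and its interval tendency (all assumed). The true odds ratio is (0.05/0.95)/(0.03/0.97) = 1.70. The unadjusted estimate averaged between 1.43 and 2.02, according to the sign and size of the correlation. With zero correlation it stayed near 1.70. The ratio of true to naive standard error ran from 0.98 to 1.26, consistent with step 2 at these lower ICCs.

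**4. Repeat examinations within a patient.** With 1.25 to 3 later examinations per patient and a within-patient ICC of 0.05 to 0.30 (assumed), DE = 1 + (k − 1) × ICC runs from 1.01 to 1.60. That formula suits a mean rate or a covariate fixed within the patient. Interval varies within the patient, and in simulation (mean 1.7 examinations per patient) the ratio of true to naive standard error for interval was 0.92 to 1.04, indistinguishable from 1. For the mean rate, the 3,773 patients with at least two follow-ups give a half-width of 1.96 × √(0.03 × 0.97 / 3,773) = 0.54 points, or 0.54 × √1.60 = 0.69 at worst, still inside the 1-point target.

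**5. The plan's guards.**

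- Section 2.3.1 repeats analyses without first follow-ups under 3 years. This addresses selective early recall, not hospital differences among those who remain. In the high-risk comparison it would remove the one-year group altogether.
- Section 2.9.1(b) checks the flat-slope reading on patients with more than one repeat examination, and cross-validates across cohorts and random subsets. A random split carries the same confounding into each part.
- Appendix 1.0 keeps a screening dataset for validation. That tests replication; it adjusts nothing.

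**The case against.** Three stronger readings are tempting, and the documents do not support them.

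- **That repeat examinations are pooled as independent.** Section 2.9.2 does not state the unit of analysis or an independence assumption, section 2.8 counts subjects, and first follow-up gives one examination per patient. The fair statement is that nothing is specified.
- **That the models ignore baseline examination quality.** The Cox models, which 2.3.1 makes central to questions 6 to 8, adjust for procedural characteristics. The logistic term lists are open-ended, and the model equations are not legible in the text reviewed. The multistate models also estimate test sensitivity.
- **That estimates are confounded towards a flat slope, with intervals too narrow.** Neither direction nor size is established. Step 3 moves the odds ratio both ways, and every ICC is assumed.

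It can also be argued that lesions found at an early repeat after a poor baseline examination really were missed, which is how the plan reads a flat slope, and it words that reading cautiously. This stands for those patients. It does not follow for well-examined patients in the same subgroup, whose yield may still rise with time. On the planning rates, an average excess of 5% − 3% = 2 points among the shorter-interval patients would hide that rise completely.

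The Intermediate Adenoma analyses are already reported (Appendix 1.0, clarification (b)), so the point bears mainly on the remaining work. That clarification applies section 2.9 to the All Adenomas study, and the yield-by-interval and high-risk comparisons at the end of 2.9.3 serve question 8.

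Finally, requiring hospital fixed effects or strata everywhere would be debatable. They discard between-hospital variation in practice, part of the information the plan relies on. The high-risk group had about 50 CRCs (reading the counts in section 2.8 in the order low, intermediate, high), or 50 / 20 = 2.5 per hospital before further accrual. This objection stands and shapes the fix.

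**Conclusion.** The point holds as a risk that the analysis text leaves uncontrolled, not as a demonstrated bias. Hospital and clustered variance are not named anywhere legible in section 2.9. Procedural covariates are named for the Cox models but not for the logistic interval models, and the high-risk interval comparison has no stated adjustment. The existing guards are useful but partial.

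Hospital clustering is the main issue. Design effects of about 1.2 to 2.4 rest on 20 hospitals of equal size, the intermediate-risk count of 7,046, and the assumed ICCs; smaller hospital differences would give less. The simulated range of 1.43 to 2.02 around 1.70 shows that bias could matter and could go either way. Within-patient clustering is secondary and probably negligible for the interval term. Power for the first follow-up contrast stays above 90% up to a design effect of 1.70 and drops to 79% only at the harshest combination, so no sample-size change is called for.

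**What to change.** 1. Carry the procedural characteristics used in 2.9.3 into the logistic models of 2.9.1 and 2.9.2 and into the yield-by-interval analyses of 2.9.3. Replace the crude high-risk CRC comparison with an adjusted Cox model. Name these covariates in the plan; the documents do not list them, so which ones are available must be confirmed.
2. Use hospital-clustered robust standard errors with a small-sample correction, since there are only about 20 clusters. Report each interval effect with and without hospital as a stratum (Cox) or effect (logistic). A material difference between the two signals confounding by hospital.
3. State the unit of analysis in 2.9.2. Where a patient contributes more than one later examination, use generalised estimating equations or patient-clustered variance, with visit number as a covariate.

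The cost is plan wording and standard software options. Confidence intervals will be somewhat wider, and the hospital-adjusted estimates use only within-hospital variation in interval, so they will be less precise where practice differs mainly between hospitals.
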